**Tolvaptan Treatment to Reverse Worsening Outpatient Heart Failure:
Possible Role of Copeptin in Identifying Responders
(TROUPER)**

NCT number NCT02476409
Document Date 03/07/2022

Study Protocol

Tolvaptan Treatment to Reverse Worsening Outpatient Heart Failure: Possible Role of Copeptin In Identifying Responders (TROUPER)

[name], MD
Principal Investigator

Co-Investigators, [name], BA, [name], ANP, ACNP, [name] on
behalf of the UNITE-HF investigative team at UNC-CH and the UNITE-HF Site Network

University of North Carolina at Chapel Hill

Version: 12.1

Version Date: 3-7-2022

1. Protocol Synopsis

Title:	Tolvaptan Treatment to Reverse Worsening Outpatient Heart Failure: Possible Role of Copeptin In Identifying Responders
Indication:	Heart Failure
Location:	Approximately 4-6 clinical centers in U.S.
Rationale:	Patients with worsening heart failure presenting in the outpatient setting represent a unique opportunity for novel approaches to decongestion that may more rapidly improve fluid status and symptoms as well as reduce the risk of hospitalization. In these patients with less severe congestion, combining the vasopressin antagonist tolvaptan with loop diuretic may represent a more effective strategy for decongestion. In addition, profiling copeptin may help identify patients in this unique population who are more likely to respond to tolvaptan.
Hypothesis:	This study is designed to test two related hypotheses 1) that the addition of oral tolvaptan to loop diuretic therapy will produce better decongestion than augmentation of loop diuretic therapy in patients presenting with worsening heart failure in the outpatient setting 2) that prespecified post hoc stratification on baseline copeptin level will be a predictor of the degree of superiority of oral tolvaptan plus loop diuretic compared to augmentation of loop diuretic.
Study Design:	This study will be a randomized, double blind, positive control, multi-center clinical trial enrolling patients who present in the outpatient setting with signs and symptoms consistent with worsening congestive heart failure. The sample size for the study is 40 patients. Candidates for the study will be identified by screening outpatients presenting with worsening heart failure. Patients who qualify for the study will be enrolled within 24 hours of identification. Patients will initiate study medication in a hospital setting and will be observed for a period of time that will depend upon their baseline serum sodium and response to study drug. In most cases patients will be observed for 8 hours. Following this observational period, patients will leave the hospital setting and the remainder of the study will consist of follow-up by outpatient visits or by telephone.
Primary Objectives:	The primary objectives of this study are to compare the effects of oral tolvaptan plus augmented loop diuretic versus augmented loop diuretic on short term changes in body weight and indices of congestion in patients presenting with worsening congestive heart failure in the outpatient setting with and without prespecified post hoc stratification based on baseline copeptin level.

**Tolvaptan Treatment to Reverse Worsening Outpatient Heart Failure
STUDY FLOW CHART**

SCREENING
Patients presenting with worsening heart failure in the outpatient setting will be considered for the study. Patients who meet study inclusion and exclusion criteria will be consented and enter the study.
RANDOMIZATION
Patients will be randomized in a 1:1 fashion to Augmentation of current daily dose of oral loop diuretic + 30 mg of oral Tolvaptan daily OR Augmentation of current daily dose of oral loop diuretic + placebo for tolvaptan. The last day of study drug administration will be Day 8 of the study.
BASELINE VISIT

 • History and physical examination, vital signs, and review of current cardiovascular medications • Serum pregnancy test • Assessment of degree of congestion present • Blood sampling for routine clinical labs and copeptin determination • Blood sampling for optional biobank for future study of biomarkers, DNA and RNA • Urine sample for future analysis 
Patients without baseline hyponatremia (serum sodium <135 mEq/L) will be observed for 8 hours in a hospital setting after dosing with study medication for assessment of vital signs and adverse events. Patients with baseline hyponatremia will be observed in a hospital setting and have repeat determination of serum sodium 6 hours after their dose of study drug. Patients with overcorrection of serum sodium (increase in serum sodium of > 6 mEq/L from baseline) will be receive D5W and have serum sodium monitored for a minimum of 24 hours (details in study protocol). Hyponatremic patients without overcorrection of serum sodium will complete observation at 8 hours.

FOLLOW-UP VISITS

Day 3 Visit, Day 8 Visit
 
 • History and physical examination, vital signs, current cardiovascular medications • Blood sampling for routine clinical labs and copeptin determination • Blood sampling for optional biobank for future study of biomarkers, DNA and RNA • Urine sample for future analysis • Changes in cardiovascular medications • Assessment of degree of congestion present • Assessment for occurrence of events related the morbidity index • Assessment for adverse events 
Day 30 Telephone Follow-up
 
 • Days of hospitalization and cause of hospitalization • Days of ED visit and reason for ED visit • Days of clinic visits and reasons for clinic visits

- Changes in cardiovascular medications
- Assessment for adverse events

2. Background and Rationale

Problem and Target Population. Worsening heart failure due to fluid overload remains a vexing problem in congestive heart failure (CHF) despite the use of evidenced-based medications dictated by guideline directed therapy. Acute decompensated heart failure is one manifestation of this general syndrome of worsening heart failure that has attracted increasing attention. Acute decompensated heart failure is on the severe end of the spectrum of the worsening heart failure syndrome and has emerged as a major public health problem associated with frequent hospitalization and a poor prognosis post discharge. However, patients presenting with worsening heart failure in the outpatient setting are also an important part of the overall decompensated heart failure syndrome. We are proposing that these patients comprise a novel clinical subset that has not been well investigated to date. Often patients presenting to the outpatient clinic with decompensated heart failure have less congestion and fluid overload than patients with acute heart failure who require hospitalization. Patients in this less ill group can often be managed as outpatients but they are at risk of developing more severe congestion and progressing to hospitalization. As efforts to reduce hospitalization for heart failure continue to intensify, the aim will be to identify interventions that more effectively relieve fluid overload and allow outpatient management without hospitalization.

The pathophysiology of the process that leads to congestion in outpatients who present with worsening heart failure is not fully delineated. However, congestion caused by sodium and water retention appears to be the major pathophysiological process underlying their decompensation. It is also well recognized these patients decompensate despite the administration of chronic diuretics including loop diuretics. Current treatment typically involves augmenting existing loop diuretic therapy and, less commonly, the addition of non-loop diuretics. However, this approach is often ineffective; hospitalization may ensue or the patient may have a poor response characterized by persistent symptoms and a slow recovery to euolemia. Despite poor outcomes with current approaches, there has been little clinical investigation of potential therapeutic strategies to improve care in this important clinical subset.

Tolvaptan Therapy. Vasopressin antagonists are a potential adjunct to current strategies for the treatment of worsening heart failure seen in the outpatient setting. Tolvaptan, a selective oral V2 vasopressin receptor antagonist, has been well studied in acute and

chronic congestive heart failure. This agent is well known to produce substantial water loss that is accompanied by a significant reduction in body weight that is especially prominent early in the treatment period. This study will test the hypothesis that acute water loss and weight reduction induced by tolvaptan will be an effective strategy, when combined with loop diuretic therapy, to reverse the volume expansion occurring in outpatients with worsening heart failure. This tolvaptan based strategy, may be an effective way to reset the patient's volume status to euolemia and thereby reduce symptoms and prevent progression to hospitalization. If this concept is correct, the addition of tolvaptan may be short-term and yet still effective.

Copeptin Guided Therapy. In addition to testing the possible novel role of tolvaptan as effective therapy in outpatients with worsening heart failure, this trial is also designed to investigate the potential role of the biomarker, copeptin, to guide patient selection for tolvaptan therapy. Copeptin or c-terminal pre-provasopressin is tightly coupled to vasopressin secretion. So this biomarker provides a reliable estimate of the extent of vasopressin activation in patients presenting with worsening heart failure. Greater activation of vasopressin could result in more water retention and promote expansion of intravascular volume; leading to more advanced congestion than that promoted by sodium retention alone. Given that the major mechanism of action of tolvaptan appears to be inhibition of vasopressin, it is possible that this drug may be more pharmacologically active in patients where greater vasopressin activation is present.

In the current study design, assessment of the association of copeptin with the therapeutic response to tolvaptan will be done post hoc. Samples for analysis of copeptin will be obtained throughout the study but assays will not be performed until after the study is completed. The proposed principal analysis of the predictive role of copeptin for tolvaptan response will be based on post hoc stratification of the study population by baseline copeptin level. The current plan is to base this post hoc stratification on the results of a recently completed pilot study of the association of pre-treatment copeptin level with the effect of tolvaptan on change in body weight in patients with chronic stable heart failure due to reduced ejection fraction.

Results from this pilot study by our group provide preliminary data to suggest that copeptin may indeed be an effective way to identify patients with heart failure who have greater response to tolvaptan. A total of 20 outpatients with chronic stable symptomatic heart failure and history reduced left ventricular ejection fraction (≤ 40) were enrolled in the pilot study. Patients were selected for later enrollment by targeting those with upper or

lower quartile copeptin levels determined during an outpatient screening period (n=10 each). Patients received a single dose of 30 mg of tolvaptan and body weight, fluid intake and urine output were monitored in a clinical research unit for 24 hours. For analysis, patients were divided into two groups using a prespecified cut point based on their baseline copeptin level determined during their study hospitalization (≥ 10 versus < 10 pmol/L). Results comparing key study variables based on this prespecified cut point approach are shown in Table 1. These findings demonstrate that change in body weight, reflecting the net aquaretic response to tolvaptan, was greater in the subgroup of patients with baseline copeptin levels ≥ 10 pmol/L.

Table 1. Changes in body weight and fluid status after tolvaptan by baseline copeptin

Study Group	All Patients	Copeptin ≥ 10 pmol/L	Copeptin < 10 pmol/L	*P value
N	20	10	10	
Baseline Copeptin (pmol/L)	13.1 ± 9.7	20.5 ± 8.7	5.7 ± 1.9	<0.001
Change in Body Weight (Kg)	-0.8 ± 1.1	-1.3 ± 1.0	-0.4 ± 1.0	0.035
Net Output (mL)	1360 ± 1881	2091 ± 1662	630 ± 1876	0.089
Total Output (mL)	6141 ± 2072	6498 ± 2328	5784 ± 1835	0.853
Total Input (mL)	4780 ± 1664	4406 ± 1398	5154 ± 1893	0.393

Values are mean \pm SD. *P Values are for comparison of copeptin groups by nonparametric analysis.

One potential implication of these pilot study results is that the contribution of water retention to the worsening chronic heart failure seen in the outpatient clinic may vary significantly. Patients with low vasopressin activation can be hypothesized to have less water retention and so that water overload may play less of a pathophysiological role than sodium retention in these patients. In contrast, if the patient's heart failure is associated with an elevation in vasopressin, there may be a greater role for water overload and therefore a better clinical response to tolvaptan therapy.

Assessment of Other Potential Markers.

The study will collect serial blood samples to allow future investigation of other potential biomarkers and Omic markers (including DNA and RNA) that may inform understanding of the decompensated heart failure state and heart failure patient response to tolvaptan therapy.

Assessment of Congestion. One of the key design features of this protocol is the choice of the primary efficacy endpoint. Years of acute heart failure research have established the difficulty of identifying a sensitive method to detect important changes in fluid status during treatment for acute decompensation. Although some have questioned the role of objective assessments of congestion like change in body weight, the work of Pang et al. shown below (Figure 1) suggests reconsideration of this measurement as a useful surrogate marker. These investigators report data from the EVEREST trial that shows a very strong link between the degree of acute weight loss and the magnitude of dyspnea relief reported by the patient after 24 hours of inpatient therapy. These findings strongly support using change in body weight as the primary efficacy endpoint for the current study.

Figure 1. Pang et al. Change in Weight versus Change in Patient Reported Dyspnea

[figure not shown]

Figure 5 Association between patient-assessed dyspnoea status and body weight change at inpatient Day 1. Note: worse includes minimally worse, moderately worse, and markedly worse. For association between weight change and treatment: $P < 0.0001$ for dyspnoea status adjusted for treatment; $P < 0.0001$ adjusted for dyspnoea status; and $P = 0.3008$ for dyspnoea-treatment interaction.

Visual Analog Scales (VAS) for Patient Assessment. Additionally, it is necessary to consider other approaches to assess fluid status that are more clinically oriented. There continues to be substantial controversy surrounding the accuracy of a number of clinical assessments to document improvement in worsening heart failure. Both the nature of the

symptom and sign assessment as well as the type of measurement used remains in dispute. However, scales that measure symptomatic dyspnea remain a major tool to quantify the effect of treatment strategies to reverse worsening heart failure. Documenting improvement in patient reported dyspnea by the 10-point VAS is generally well accepted as evidence of clinical effectiveness of an intervention. This scale has been used in a number of acute heart failure trials. Therefore changes in the VAS dyspnea scale from baseline to Visit 2 is designated as the highest priority secondary endpoint in this trial. It is important to note that due to measurement variability, VAS and Likert scales are relatively insensitive ways to determine changes in patient symptoms and substantial sample sizes are needed to have power to detect significant differences especially between placebo and drug groups. The present study sample size is not adequate for this purpose. However, observed changes may be compared to those seen in larger acute heart failure trials to give hypothesis generating signals of tolvaptan efficacy.

Changes in Loop Diuretic to Reflect Clinical Status. Recent work with tolvaptan has documented that background loop diuretic therapy does not remain the same in tolvaptan and placebo groups throughout the study period. Although well recognized to be a confounder of the interpretation of the efficacy of tolvaptan therapy in addition to loop diuretics, studies to date have not been well designed to capture detailed information on changes in loop and other diuretics during the study period. In contrast, the present study is designed to collect detailed information on type of diuretic as well as dose in conjunction with extensive clinical assessments at specific visits during the study. This will assist in correlation of clinical findings with changes in diuretic dosing in the study arms.

In addition, our extensive clinical experience with outpatients treated for worsening heart failure since the inception of the TROUPER study has clearly demonstrated the clinical relevance of changes in loop diuretics during treatment for decompensation. This experience strongly suggests that increases in loop dose during Visit 2 would reflect worsening congestion while a decision to reduce loop dose during Visit 2 would indicate improvement in volume status and less congestion. Therefore, assessments of change in loop diuretic dosing at Visit 2 are designated as key secondary endpoints in this trial. Three assessments of change in loop diuretic will be made during analysis of study results: 1) change from baseline to 48 hours in loop diuretic dose (with loop diuretic dosing standardized on milligrams (mg) of furosemide equivalent), 2) whether loop diuretic dose was changed at 48 hours using a dichotomous approach and 3) changes in loop diuretic which account for whether loop diuretic was decreased, increased or unchanged. Details

of this analysis and the respective priority of these key secondary endpoints related to changes in loop diuretic at Visit 2 are presented later in the statistical analysis plan section of this protocol.

Heart Failure Clinical Status Assessments. This study also affords the opportunity to collect a substantial amount of information on various indices of heart failure status in this unique clinical population. Data remain limited on the clinical characteristics and clinical course of patients with outpatient worsening of heart failure. The study will use a novel version of the 10-point VAS scale for patient reported congestion based on the patient's self report of their perception of the extent of fluid overload present. The study investigator also will complete a VAS congestion scale based on their perception. Finally, reported changes in fluid status will also be assessed by the Likert scale method with data collected from patients and as observed by study investigators. A substantial amount of information was collected on a variety of signs and symptoms of heart failure status including detailed assessment of congestion and physical limitation during the follow-up period. Future analyses of these data will help to better understand the clinical picture and course of patients with outpatient worsening of heart failure.

Clinical Outcomes. Assessment of the effect of study treatments on occurrence of worsening heart failure as reflected by extra clinic visits, increases in diuretic treatment and hospitalization is of interest in this unique study population. The small sample size of this pilot trial makes it unlikely that this issue could be adequately addressed by the current study. However, information on these adverse clinical outcomes will be collected as part of the protocol.

Modifications to Original Study Statistical Analysis Plan. A number of modifications were made to the original statistical analysis plan for the study. Secondary efficacy endpoints were revised to reflect 1) knowledge gained since the design of the study concerning the assessment of worsening heart failure, 2) the results of analyses of blinded, aggregate study data related to clinical metrics of worsening heart failure collected in the trial and 3) refinement of the analysis of the primary endpoint related to baseline copeptin and clarification of the analysis of the association of change in body weight with baseline copeptin in the two randomized arms of the study. In addition, to reduce the effect of multiple testing, a limited number of secondary endpoints were specified. These finalized secondary outcomes were ordered according to their clinical importance. Blinded review of adverse outcomes revealed that events related to worsening heart failure were uncommon during the treatment period. Thus the tertiary endpoint, clinical composite of morbidity, was

removed due to lack of power to address between group differences. Finally, the approach to exploratory endpoints was refined to emphasize future aggregate analyses of detailed data collected on heart failure characteristics and the clinical course of this unique population of heart failure patients. The primary endpoint of the study was unchanged. Changes to the original statistical analysis plan were made before the study was unblinded. All changes were made in consultation and agreed upon by the statistician conducting study data analysis.

3. Study Objectives and Hypotheses

Hypotheses. This study is designed to test two related hypotheses 1) that the addition of oral tolvaptan to augmented loop diuretic therapy will produce better decongestion than augmentation of loop diuretic therapy alone in patients presenting with worsening heart failure in the outpatient setting and 2) that prespecified post hoc stratification based on baseline copeptin level will be a predictor of the degree of superiority of oral tolvaptan plus augmented loop diuretic compared to augmentation of loop diuretic alone.

Objectives. This study is designed to address the following objectives:

The objectives of this study will be to compare the effects of oral tolvaptan plus augmented loop diuretic versus augmented loop diuretic on 1) short term changes in body weight with and without stratification for baseline copeptin and 2) indices of congestion in patients presenting with worsening congestive heart failure in the outpatient setting with and without prespecified post hoc stratification based on baseline copeptin level.

4. Study Overview and Patient Cohort

This study will be a randomized, double blind, positive control, multi-center clinical trial enrolling patients who present in the outpatient setting with signs and symptoms consistent with worsening congestive heart failure. The sample size for the study is 40 patients. Candidates for the study will be identified by screening outpatients presenting with worsening heart failure. Patients who qualify and consent for the study will be enrolled within 24 hours of identification. Patients will be observed in a hospital setting following the initial administration of randomized therapy as outlined in detail below. Assuming they tolerate study treatment during this observation period, patients will leave the hospital setting and the remainder of the study will consist of observation during outpatient visits or telephone follow-up to assess response to randomized therapy. Patients will receive study medication through Day 8 of the study.

4.1 Inclusion and Exclusion Criteria

Inclusion Criteria

- ≥ 18 years of age
- Presenting to clinic with worsening heart failure due to congestion (fluid overload)
 - Patient reported worsening fluid overload based on perception of edema and/or weight gain

With at least one of the following symptoms

- Worsening dyspnea on exertion or fatigue
- Worsening orthopnea or PND
- Perception of abdominal and/or lower extremity edema
- Early satiety and/or decreased appetite

And at least one of the following signs

- Lower extremity edema
- Ascites
- Elevated JVD
- Pulmonary rales
- Daily oral dose of loop diuretic
- Prior history of heart failure with this diagnosis for at least 1 month with preserved or reduced left ventricular ejection fraction
- Signed informed consent

Exclusion Criteria

- Patients with symptomatic hyponatremia will be excluded from the study.
- Patients with severe hyponatremia, defined as serum sodium < 125 mEq/L at the time of screening, will be excluded regardless of whether they are symptomatic or not.
- Patients with the following predisposing factors for osmotic demyelinating syndrome (ODS), assessed by the study investigator judgment, will be excluded: chronic alcoholism at the time of study, severe liver disease, marked malnutrition, and risk for chronic hypoxia.
- Patients currently undergoing renal replacement therapy
- Planned hospitalization for acute heart failure
- History of primary significant liver disease or acute hepatic failure, as defined by the investigator

- Hemodynamically significant arrhythmias
- ACS or acute myocardial infarction within 4 weeks prior to study entry
- Active myocarditis
- Hypertrophic obstructive, restrictive, or constrictive cardiomyopathy
- Severe stenotic valvular disease amendable to surgical treatment
- Complex congenital heart disease
- Constrictive pericarditis
- Clinical evidence of digoxin toxicity
- History of adverse reaction or clinical contraindication to tolvaptan
 - Concomitant use of strong CYP3A4 inhibitors
 - Inability of patient to sense and/or respond to thirst
 - History of hypersensitivity to tolvaptan
 - Patient is anuric
- Enrollment or planned enrollment in another randomized clinical trial during the study period
- Pregnant or breast-feeding
- Inability to comply with planned study procedures

5. Study Design

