While there is no question that overcorrection of serum sodium by the criteria of an increase of > 12 mEq/L of serum sodium may rarely occur with tolvaptan therapy, the frequency with which ODS occurs in association with tolvaptan therapy remains disputed. None of the 5 patients in the SALT trials who has an increase in serum sodium of > 12 mEq/L experienced ODS (nor did any other patient in the SALT trials). No cases of ODS have been reported in patients treated with tolvaptan in randomized clinical trials including approximately 2,000 patients with heart failure. The FDA Package Insert for tolvaptan indicates that cases of ODS have been reported post marketing but the exact language in

the text concludes that the anecdotal nature of these reports does not permit assignment of causal role for tolvaptan. One example of confounding that may occur in the post marketing data is concomitant therapy with hypertonic saline. Simultaneously treatment with both tolvaptan and hypertonic saline is contraindicated, would significantly increase the risk of overcorrection and will not occur in this study. It is important to note that clinical series have found that the development of ODS may be low in the setting of overcorrection.

Implications for the Present Study. Given the study sample size of 40 patients and the planned exclusion of patients with serum sodium < 125 mEq/L, approximately 3 to 4 patients could be expected to be enrolled with hyponatremia. The low rate of overcorrection observed in the SALT Trials suggests, that even in the setting of hyponatremia, the risk of a single study patients experiencing overcorrection of sodium in response to tolvaptan would be low.

Minimizing Risk of Overcorrection of Sodium. Although the risk of overcorrection of serum sodium is low in patients with heart failure, it is appropriate to take steps to reduce the risk of this potentially very serious and rarely fatal complication.

During Screening

- 1- Patients with symptomatic hyponatremia will be excluded from the study.
- 2- Patients with severe hyponatremia, defined as serum sodium < 125 mEq/L at the time of screening, will be excluded regardless of whether they are symptomatic or not.
- 3- Patients with the following predisposing factors for ODS, assessed by the study investigator judgment, will be excluded: chronic alcoholism at the time of study, severe liver disease, marked malnutrition, and risk for chronic hypoxia.

Randomization - Initial Dose of Study Drug

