11. Patients found to be hyponatremic will also be monitored for development of symptoms during the study related to reduced serum sodium. As a precaution, patients with symptomatic hyponatremia are excluded from the study. Patients with heart failure who present with hyponatremia are very commonly asymptomatic and the condition is chronic and does require therapy to reverse the hyponatremia per se. Patients with heart failure and chronic hyponatremia rarely become symptomatic. Patients enrolled in the study with asymptomatic hyponatremia will be cautioned to monitor for changes in mental status, nausea, and lethargy between their baseline visit and follow-up visits. Patients will be instructed to contact the study investigators should these symptoms develop and they will be seen for follow-up evaluation as needed.

Hepatic Toxicity. The FDA proposed label changed for tolvaptan in 2013. These changes concerning tolvaptan use indicated that the drug should not be used for longer than 30 days and should not be used in patients with underlying liver disease. These changes were made after 3 cases of suspected liver injury with Tolvaptan were identified in the TEMPO study. TEMPO studied a significantly higher tolvaptan dose (60 mg per day and titrated up to 120 mg per day) and a longer duration of treatment (36 months) than in the planned study (30 mg for 8 doses – with 8 days of exposure). The patient population in TEMPO (Autosomal Dominant Polycystic Kidney Disease) is different than the one proposed for this study. The liver abnormalities occurred after at least 3 months of treatment and all 3 patients improved following discontinuation of treatment. The study protocol for this trial will exclude patients with known underlying liver disease to be consistent with the revised FDA labeling.

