Appendix A: Schedule of Study Assessments

[figure not shown]
Assessment or Procedure	Screen	Baseline	8 to 24 [†] hours	Day 3	Day 8	Day 30
Informed Consent	X					
Review of Inclusion and Exclusion Criteria	X					
Serum pregnancy test as applicable		X				
Screening electrolytes, renal and liver function tests	X					
Directed History and Physical Examination		X		X	X	
Vital signs		X	X	X	X	
Body Weight		X		X	X	
Current Cardiovascular Meds		X		X	X	X
Blood sampling for Serum Creatinine, BUN, electrolytes, serum osmolarity and copeptin		X	X*	X	X	
Blood Sampling – for Other biomarkers and Omics		X		X	X	
Blood Sampling – Whole blood		X				
Urine Sampling		X		X	X	
Adverse Events Assessment			X	X	X	X
Assessment of Congestion and Dyspnea		X		X	X	
Changes in Cardiovascular Meds			X	X	X	X
Morbidity Assessment				X	X	X

* Blood sampling will be dependent up baseline hyponatremia or change during observation. † It is possible that a rare patient may have to remain under observation for more than 24 hours before their serum sodium is < 12 mEq/L based on determinations from serial blood samples.

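### Section 10.1 says patients with known underlying liver disease are excluded, but the liver item in section 4.1 is narrower and does not deliver that exclusion

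*Combined protocol and SAP*

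**What the plan says.** Section 4.1, the eligibility list that sites apply, touches on liver disease in two exclusion items.

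- The liver item itself: "History of primary significant liver disease or acute hepatic failure, as defined by the investigator".
- The item on predisposing factors for ODS, left to investigator judgment. It lists "chronic alcoholism at the time of study, severe liver disease, marked malnutrition, and risk for chronic hypoxia". The same list appears again in section 10.1 among the screening steps against sodium overcorrection.

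Section 4.1 also has a general item, "History of adverse reaction or clinical contraindication to tolvaptan". Its sub-items are strong CYP3A4 inhibitors, inability to sense or respond to thirst, hypersensitivity and anuria.

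Section 10.1, under Hepatic Toxicity, reports a 2013 label change, part of which was that tolvaptan "should not be used in patients with underlying liver disease". It closes with a statement about this trial: "The study protocol for this trial will exclude patients with known underlying liver disease to be consistent with the revised FDA labeling".

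Appendix A schedules "Screening electrolytes, renal and liver function tests" in the screening column, the same column as the review of the inclusion and exclusion criteria. No section attaches a cut-off to the liver results.

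**The concern.** Section 10.1 tells ethics boards, sites and other readers that a defined group is not in the trial, and gives agreement with the label as the reason. The criteria that decide who enters are narrower. A site can follow section 4.1 to the letter, commit no protocol deviation, and still dose a patient whom the safety section describes as excluded. What is at stake is whether a stated safety exclusion, and the claim of label consistency attached to it, are true of the trial as the protocol defines it.

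**Working it through.** There is no figure to reproduce. The check sets every liver-related eligibility statement side by side and asks whether the section 4.1 items, taken together, cover the group named in section 10.1.

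| Place | Who is excluded | Limits on the exclusion |
|---|---|---|
| 10.1, Hepatic Toxicity | Known underlying liver disease | None on severity or cause; no reference to investigator judgment |
| 4.1, liver item | Liver disease, or acute hepatic failure | Disease must be primary and significant; the investigator defines this |
| 4.1, ODS item (repeated in 10.1) | Liver disease as an ODS risk factor | Must be severe; investigator judgment |
| 4.1, contraindication item | Prior adverse reaction or contraindication to tolvaptan | Liver not among the sub-items |
| Appendix A, screening | Liver function tests drawn | No cut-off or stated rule |

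**Step 1: known liver disease judged not significant.** It falls under the section 10.1 statement, which sets no threshold of severity. It is outside the liver item, which requires significance. It is outside the ODS item unless it is also judged severe.

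**Step 2: known liver disease that is not primary.** It falls under section 10.1 if that statement is read as written, since no cause is specified. It is outside the liver item because of the word primary, and outside the ODS item unless severe. Section 10.1 does not say whether liver effects of heart failure count as underlying liver disease, so this step depends on the plain wording. Step 1 does not.

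**Step 3: does the contraindication item close the gap?** An investigator could treat the label statement as a contraindication and exclude the patient that way. Nothing in the item requires this. The sub-items leave out the liver, and a separate, more specific liver item exists, which a site would naturally take as governing.

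**Step 4: do the screening tests close the gap?** They are available when eligibility is reviewed and can inform the investigator's judgment under the liver item. They do not widen that item: a patient already known to have liver disease, and judged not to have significant disease, still passes.

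**Result.** The group in section 10.1 is wider than anything section 4.1 is bound to exclude. The difference consists of patients with known liver disease that the investigator judges not significant, or not primary, and not severe.

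**The case against.** The best reply is that this is loose summary wording. Section 10.1 is a risk narrative, sites enrol from section 4.1, and the sentence can be read as shorthand for the list. It is correct that sites are not working from two rival lists. Variation between sites in what counts as significant comes from the investigator judgment in section 4.1, which is an ordinary feature of eligibility criteria. But the sentence says what the protocol will exclude and ties that to the label, so it has to be accurate.

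Several stronger readings are tempting and should not be adopted.

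- *The hepatic safety case depends on this exclusion.* A reader might infer this, but section 10.1 first gives other grounds. The liver cases arose at 60 mg titrated up to 120 mg per day over 36 months, against 30 mg for 8 days here. The population was different, the abnormalities appeared after at least 3 months, and all 3 patients improved after stopping. The exclusion comes last.
- *The severe-disease wording also contradicts section 10.1.* It does not. That item begins "Patients with the following predisposing factors for ODS, assessed by the study investigator judgment, will be excluded", so it concerns a different risk from hepatotoxicity.
- *The screening liver tests are not used.* The documents do not show this. The absence of a numeric cut-off does not stop the investigator from using the results, and an abnormal test is not the same as known liver disease.
- *A few of the 40 patients are affected.* Any count needs an assumed prevalence. At 2.5% to 10%, for example, 40 × 0.025 = 1 and 40 × 0.10 = 4. The documents support no prevalence, the arithmetic supposes that no investigator would exclude such a patient on other grounds, and zero fits the text equally well.
- *Ineligible patients were treated.* Nothing in the documents shows that any such patient was enrolled.

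It is also fair to say that the word primary may be deliberate. The trial recruits fluid-overloaded patients and accepts ascites as a qualifying sign, so the word may be there to keep the target population eligible. That would explain the section 4.1 wording, but it would leave the section 10.1 statement wrong.

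**Conclusion.** The inconsistency is real. Section 10.1 states an exclusion of known underlying liver disease without qualification, and section 4.1 excludes a narrower group that depends on the investigator's definition. Patients in between can be enrolled in full compliance with section 4.1. The conclusion rests only on the wording and on the usual assumption that section 4.1 is the operative list. It is firmest for liver disease judged not significant. For non-primary disease it also assumes that section 10.1 means what it says about cause.

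The number of patients concerned cannot be estimated from the documents. Sample size, power, the primary endpoint and the analysis are unaffected. The point matters because a stated safety exclusion and its label-consistency claim are not carried out by the criteria.

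**What to change.** Reconcile the liver item in section 4.1 with the closing sentence of Hepatic Toxicity in section 10.1 so that both describe the same exclusion. There are two ways to do this, and the choice is a clinical one for the sponsor and investigators:

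- revise the section 4.1 item so that it delivers what section 10.1 states; or
- correct the exclusion and label-consistency statement in section 10.1 so that it describes what section 4.1 excludes.

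Whichever is chosen, the text should make clear whether liver disease that is not primary is covered. The severe liver disease entry among the ODS factors, in sections 4.1 and 10.1, serves another purpose and can stay as it is.

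The cost is a wording change. If the broader exclusion is kept there may be more screen failures, and the documents do not allow their number to be estimated. If enrolment has already closed when this is acted on, a change to section 4.1 can no longer alter who entered. The section 10.1 statement should then be corrected, and the trial report should say which criterion was applied.
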